8.1.2.3. Suspected Unexpected Serious Adverse Reactions

Suspected unexpected serious adverse reactions (SUSARs) are SAEs that are not listed in the Development Core Safety Information (galunisertib IB Section 7) or Reference Safety Information for Adverse Drug Reactions (nivolumab IB Section 5.6) and that the investigator identifies as related to study drug or procedure. The United States 21 CFR 312.32, the European Union Clinical Trial Directive 2001/20/EC, and the associated detailed guidances or national regulatory requirements in participating countries require the reporting of SUSARs. Lilly has procedures that will be followed for the recording and expedited reporting of SUSARs that are consistent with global regulatory regulations and the associated detailed guidances.

8.1.2.4. Summary of AE/SAE Reporting Guidelines

The AE and SAE reporting guidelines are summarised in [Table JBEF.8.1](#).

Table JBEF.8.1. Adverse Event and Serious Adverse Reporting Guidelines for Study H9H-MC-JBEF

Timing	Types of AEs/SAEs Reported	Collection Database	Lilly Safety System
Prestudy (baseline assessments) (Starts at the signing of informed consent and ends just before the first dose of study drug)	Preexisting conditions All AEs All SAEs regardless of relatedness	x x x	x
On therapy (Starts at first dose of study drug[s] and ends at last dose of study drug[s])	All AEs All SAEs regardless of relatedness	x x	x
Follow-up visits (Starts just after the last dose of combination treatment and ends when end of study safety assessments are completed [2 visits at approximately 30 and 100 days after last dose of study drugs])	All AEs All SAEs regardless of relatedness	x x	x
Subsequent follow-up visits, if necessary for patient monitoring	Ongoing AEs possibly related to study drug(s) or protocol procedures All SAEs related to protocol procedures or study drug	x x	x
Patient no longer on study	All SAEs related to protocol procedures or study drug that the investigator becomes aware of		x

Abbreviations: AEs = adverse events; SAEs = serious adverse events.

8.1.3. Other Safety Measures

8.1.3.1. Detection of Aneurysm Formation of the Ascending Aorta and Aortic Arch (Thoracic View)

MRI or CT scan with contrast of the chest will be performed and assessed locally at the site at baseline screening and every 6 months. For Germany, MRI of the chest is an acceptable alternative and may be used instead of CT scans. Each of the imaging techniques are used to detect aneurysms of the ascending aorta or aortic arch and must follow institutional guidelines. Once the method of assessment is chosen for a given patient, it must be used throughout the study for that patient.

8.1.3.2. Electrocardiograms

For each patient, a 12-lead ECG will be collected as indicated in [Attachment 1](#) and [Attachment 4](#). Please see [Attachment 4](#) for specific ECG times matched with PK blood draws.

For each patient, 12-lead digital ECGs will be obtained as single ECGs according to the study schedule ([Attachment 1](#)). Patients must be supine for approximately 5 to 10 minutes before ECG collection and remain supine during ECG collection. ECGs may be obtained at additional times

when deemed clinically necessary. Collection of more ECGs than expected at a particular time point is allowed when needed to ensure high-quality records.

ECGs will be interpreted by a qualified physician (the investigator or qualified designee) at the site as soon after the time of ECG collection as possible and, ideally, while the patient is still present, to determine whether the patient meets entry criteria and for immediate patient management, should any clinically relevant findings be identified.

If a clinically significant quantitative or qualitative change from baseline is identified after enrolment, the investigator will assess the patient for symptoms (for example, palpitations, near syncope, syncope) and to determine if the patient can continue in the study. The investigator or qualified designee will be responsible for determining if any change in patient management is needed and must document his/her review of the ECG printed at the time of evaluation.

All digital ECGs will be electronically transmitted to a central ECG laboratory designated by Lilly. A cardiologist at the central ECG laboratory will then conduct a full overread on the ECG (including all intervals); a report based on data from this analysis will be issued to the investigative site. All data from the overreads will be placed in the Lilly database for analytical and study-report purposes.

It is recognised that ECG interpretations by the investigator (or qualified designee) and by the cardiologist at the central ECG laboratory may be different. When there are differences in ECG interpretation between the investigator (or qualified designee) and the cardiologist at the central ECG laboratory, the investigator (or qualified designee) interpretation will be used for study entry and immediate subject management. Interpretations from the cardiologist at the central ECG laboratory will be used for data analysis and report-writing purposes.

The investigator (or qualified designee) must document his/her review of the ECG printed at the time of evaluation, the final overread ECG report issued by the central ECG laboratory, and any alert reports.

Other safety measures include assessments of physical examinations, preexisting conditions, transfusions and hospitalisations, and AEs. Patients will be assessed before each visit by using the CTCAE v4.0.

8.1.3.3. Echocardiography/Doppler

Echocardiography with Doppler will be locally assessed for enrolment and safety decisions by physicians or a team of people who are qualified by experience or training. Individuals so qualified must be identified at each site. The same person should be responsible for reading the ECHOs on any individual study patient. ECHOs will be as indicated in [Attachment 1](#). The ECHO will be electronically transmitted to a designated central laboratory for analysis. Data will be interpreted by the vendor cardiologist for data analysis and study report writing purposes.

Cardiotoxicity: ECHO/Doppler imaging will include the following assessments and other standard evaluations (see [Attachment 10](#)): an increase of 1 or more grades in the semiquantitative valvular insufficiency, LV function, or right ventricular systolic pressure (normal, mild, moderate, severe based on local laboratory limits). After a normal baseline

ECHO, if a subsequent ECHO demonstrates an abnormality, then a repeat ECHO should be performed after 14 days. If results confirm the abnormality at repeat ECHO, then the patient will be discontinued from study treatment. If findings are normal, then the patient will continue treatment per study protocol. If patient has clinically significant cardiac findings at 30-day follow-up visit, ECHO will be repeated every 2 cycles (approximately every 2 months). If no clinically significant cardiac findings at the last cardiac assessment conducted within the last 30 days and patient has started another treatment, 30-day follow-up visit will not be performed. If no clinically significant cardiac findings at 30-day follow-up visit, 1 more ECHO will be performed after 2 months unless the patient is receiving another treatment. If the patient is receiving another form of treatment, further cardiac assessments will not be performed.

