7.2.4.1.3. Discontinuation from Galunisertib

If dosing is delayed for galunisertib-related AEs such that the patient cannot resume galunisertib treatment by Day 1 of the next cycle, the patient should be withdrawn from galunisertib. In the Phase 1b part, inpatient dose reduction is permitted for a DLT if a lower dose of galunisertib has been established to be safe in combination with nivolumab, the patient has recovered by Day 1 of the next cycle, and the patient, in the opinion of the investigator and the Lilly physician, is deriving benefit. In the Phase 2 part only, patients who do recover by Day 1 of the next cycle may have the dosage reduced to the next lower (Phase 1b) dose level (see [Table JBEF.6.1](#)). If the Phase 2 galunisertib dose is 50 mg QD, no dose reduction will be allowed. If in the investigator's opinion the toxicity is related to both study drugs, both drugs should be withheld.

If moderate or severe heart valve toxicities are observed or a patient develops an aneurysm, the patient must immediately be discontinued from galunisertib treatment (for definitions see [Attachment 10](#), including references on the ECHO assessment based on the Guidelines of the American and European Societies of Cardiac Echocardiography). These events will be considered serious AEs (SAEs) and should be reported to Lilly per standard SAE reporting requirements ([Table JBEF.8.1](#)). Exceptions to this rule must be approved by the ERBs and Lilly.

Patients with combined Grade 2 AST/ALT AND total bilirubin values meeting discontinuation parameters should have treatment permanently discontinued.

If a patient experiences an AE that requires the patient be discontinued from galunisertib, the patient should continue on nivolumab (if the patient has not previously met discontinuation criteria for nivolumab). If in the investigator's opinion the toxicity is related to both study drugs, both drugs should be held.

7.2.4.2. Nivolumab Dose Adjustments and Delays, Criteria for Resumption of Nivolumab Treatment, and Discontinuation in Phase 1b and 2

Inpatient dose escalations or reductions of nivolumab are not allowed in either Phase 1b or Phase 2.

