ECHO								X					*	X		Performed every other cycle within 5 days of when next cycle begins, beginning at the end of Cycle 2 (eg, Cycle 2 Days 23-28=*). Must be done predose. After a normal baseline ECHO, if a subsequent ECHO demonstrates an abnormality, then a repeat ECHO should be performed after 14 days. If results confirm the abnormality at repeat ECHO, then the patient will be discontinued from study treatment. If findings are normal, then the patient will continue treatment per study protocol. If patient has clinically significant cardiac findings at 30-day FUP Visit, ECHO will be repeated every 2 cycles (approximately every 2 months). If no clinically significant cardiac findings at the last cardiac assessment conducted within the last 30 days and patient has started another treatment, 30-day FUP Visit will not be performed. If no clinically significant cardiac findings at 30-day FUP Visit, 1 more ECHO will be performed after 2 months unless the patient is receiving another treatment. If the patient is receiving another form of treatment, further cardiac assessments will not be performed.

During and Post-Study Assessments—Phase 1b Dose Escalation

Relative Week Within a Cycle	Cycle 1				Cycle 2				Cycle 3-n				Follow-Up (days)			Comments	
	1	2	3	4	1	2	3	4	1	2	3	4	Short-term		Long-term ^c		
	1	8	15	22	1	8	15	22	1	8	15	22	30 ^b	100			
MRI/CT scan (of chest) with contrast																**	Every 6 months during treatment (eg, just prior to beginning Cycle 6=**). If there were no clinically significant findings at the last assessment conducted within the last 30 days and the patient has started another treatment, 30-Day FUP Visit MRI or CT scan with contrast will not be performed.
Haematology	X		X		X		X		X		X		X	X			See Attachment 2.
Serum chemistry	X	X*	X	X*	X	X*	X	X*	X		X		X	X			*Only performed if the last assessment prior to this assessment had an elevated value for liver function compared to baseline. See Section 8.1.4.
HBV DNA	X		X		X		X		X								All patients to be tested. Peripheral blood. Predose.
HCV RNA	X		X		X		X		X								All patients to be tested. Peripheral blood. Predose.
HCC antiviral activity									X								HCC patients only. Peripheral blood collection for assessment of qHBsAg. Predose Day 1 at every other cycle (Cycles, 3, 5, n).
CTCAE v 4.03 Grading	X		X		X		X		X		X		X	X	X		Refer to Section 8.1.2.4 for reporting guidelines.
Concomitant meds	X		X		X		X		X		X		X	X	X		Throughout study as needed.

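### The 14-day ECHO repeat rule (8.1.3.3 and both Attachment 1 ECHO rows) has no severity limit and is not reconciled with the immediate galunisertib stop in 7.2.4.1.3

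*Protocol*

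**What the plan says.** Protocol 8.1.3.3 lists what the ECHO/Doppler examination is to look for: "an increase of 1 or more grades in the semiquantitative valvular insufficiency, LV function, or right ventricular systolic pressure (normal, mild, moderate, severe", judged against local limits. The paragraph then gives one rule for what follows an on-study finding in a patient whose baseline ECHO was normal: "if a subsequent ECHO demonstrates an abnormality, then a repeat ECHO should be performed after 14 days". The Phase 1b and Phase 2 ECHO rows of Attachment 1 carry the same wording. Two outcomes follow. The first is "If results confirm the abnormality at repeat ECHO, then the patient will be discontinued from study treatment". The second is "If findings are normal, then the patient will continue treatment per study protocol". None of the three places limits the rule by severity or says whether dosing is held while the repeat is awaited.

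Protocol 7.2.4.1.3 has its own rule: "If moderate or severe heart valve toxicities are observed or a patient develops an aneurysm, the patient must immediately be discontinued from galunisertib treatment". Its definitions come from Attachment 10, "including references on the ECHO assessment based on the Guidelines of the American and European Societies of Cardiac Echocardiography". These events are treated as serious adverse events, and "Exceptions to this rule must be approved by the ERBs and Lilly". The same section says that a patient taken off galunisertib for an adverse event should continue nivolumab, and that both drugs should be held if the investigator relates the toxicity to both.

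**The concern.** A new moderate or severe valve toxicity in a patient whose baseline ECHO was normal falls under both rules. One stops galunisertib at once. The other stops treatment only after confirmation, and its instruction to continue after a normal repeat reads as though nothing had been stopped. They also differ on what allows the patient to go on: a normal repeat in one, ERB and sponsor approval in the other.

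A site acting on an ECHO result will probably open the ECHO section or the schedule row, and neither mentions the immediate stop. It could therefore delay a mandatory safety stop, or take a normal repeat as enough to carry on. Safety is the primary endpoint, and Attachment 10 gives the cardiac safety of galunisertib as the reason for the repeated ECHOs.

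The backstops are partial:

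- The 24-hour SAE report (8.1.2.1) helps only if the site already treats the finding as a 7.2.4.1.3 event.
- In Table JBEF.7.1, the row that could catch a valve finding needs CTCAE Grade 3 or 4, and the protocol does not tie a moderate valve finding to a CTCAE grade.
- Under 8.1.3.3 the central ECHO read serves analysis and reporting; safety decisions rest on the local read.

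**Working it through.** **The two rules side by side**

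| | 8.1.3.3 and both ECHO rows | 7.2.4.1.3 |
|---|---|---|
| Trigger | Any abnormality after a normal baseline | Moderate or severe valve toxicity, or an aneurysm |
| When to stop | Once the repeat confirms it | At once |
| What stops | Study treatment | Galunisertib; nivolumab normally goes on |
| What allows galunisertib to go on | A normal repeat | ERB and sponsor approval |
| Points to | 8.1.3.3: Attachments 1 and 10; the rows cite neither section | Attachment 10, Table JBEF.8.1 |

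The shared pointer, Attachment 10, defines imaging normality. It has no stopping or precedence rule.

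**Aneurysm.** The overlap here is narrow. Exclusion criterion 21 lists heart aneurysm among ECHO abnormalities, but 8.1.3.3 does not name it, and 8.1.3.1 assigns the ascending aorta and arch to MRI or CT. The overlap exists only for an aneurysm seen on ECHO.

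**Possible exposure during the wait.** The plan states no figure to reproduce. Inputs:

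- 28-day cycle, galunisertib on Days 1 to 14 (7.2.1)
- ECHO on Cycle 2 Days 23 to 28 (the example in the ECHO rows)
- repeat after 14 days (8.1.3.3)
- visit window ±3 days (Attachment 1, footnote a)

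Assumptions: dosing continues while the repeat is awaited, Cycle 3 starts on time, and the repeat is done before that day's dose.

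Let e be the Cycle 2 day of the ECHO and g the days to the repeat. The repeat falls on Cycle 3 Day r = e + g − 28. Dosing days before it are the smaller of r − 1 and 14.

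| e | g | r | Dosing days | Share of 14-day block | BID doses |
|---|---|---|---|---|---|
| 23 | 14 | 23 + 14 − 28 = 9 | 8 | 8/14 = 57% | 16 |
| 28 | 14 | 28 + 14 − 28 = 14 | 13 | 13/14 = 93% | 26 |
| 23 | 11 (14 − 3) | 23 + 11 − 28 = 6 | 5 | 5/14 = 36% | 10 |
| 28 | 17 (14 + 3) | 28 + 17 − 28 = 17 | 14 | 14/14 = 100% | 28 |

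At 50 mg QD the number of doses equals the number of days. If galunisertib is stopped at the first ECHO, the answer is 0, because Days 23 to 28 lie in the off period (Days 15 to 28).

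**The case against.** The best reply is that the two rules can be obeyed together. They stop different things: 7.2.4.1.3 stops galunisertib, whereas 8.1.3.3 discontinues study treatment, which under the definition in 6.2.4 plausibly includes nivolumab. A site can stop galunisertib at once, repeat the ECHO at 14 days, and then decide about nivolumab. Ordinary reading also favours 7.2.4.1.3: it is the more specific rule, it is mandatory, and it has a closed exception route, while the repeat is something that should be done. Section 6.3.2 sends galunisertib discontinuation for unacceptable toxicity to 7.2.4.1.3, and continuing under the study protocol can be read as including that section. Because the scheduled ECHO falls in the off period, a site may have some days to apply the stop before the next dose.

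All of this stands as a reasonable reading, and it rules out two stronger ones that a reader might infer. The first is that the rules flatly contradict each other; the stop-and-repeat reading shows that they need not. The second is that the protocol tells sites to keep dosing during the wait; it does not, and continued dosing is at most implied by the word continue.

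What the reply does not remove is the gap itself. No sentence ranks the rules, states the combined reading or links the sections, and the ECHO rule taken alone gives a complete instruction that leads elsewhere.

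The scope difference also limits the remedy. Confining the 14-day step to mild findings would drop the repeat for the worse ones. A confirmed mild abnormality would then end all study treatment, while a severe one would stop only galunisertib.

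**Conclusion.** The concern holds as an unresolved overlap between two safety rules. After a normal baseline ECHO, the repeat rule in 8.1.3.3 and both ECHO rows covers abnormalities of any severity, and nothing there tells the site that moderate or severe valve toxicity (or an aneurysm seen on ECHO) already requires galunisertib to stop. That the cross-reference and the severity limit are missing is certain from the current text.

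The size is conditional. Per affected patient, a site following only the ECHO rule could give 8 to 13 further dosing days, or 5 to 14 with the visit window, against 0 if galunisertib is stopped or held. This is a possible range, not an expected exposure. It rests on dosing continuing during the wait and on Cycle 3 starting on time, and the documents do not show how many patients would be affected. A protocol change is still worthwhile, because a mandatory stop for an event that the protocol itself classes as serious should not depend on site inference.

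**What to change.** 1. In 8.1.3.3 and both Attachment 1 ECHO rows, state that moderate or severe heart valve toxicity, or an aneurysm, means immediate galunisertib discontinuation under 7.2.4.1.3. The stop does not wait for the repeat and stands whatever the repeat shows, unless the ERBs and the sponsor approve an exception.
2. Keep the 14-day repeat for all abnormalities. Where galunisertib has already stopped, state that a confirmed abnormality also ends the remaining study treatment (nivolumab), as 8.1.3.3 now provides, despite the general instruction in 7.2.4.1.3 to continue nivolumab. A worse finding then never gets a narrower stop than a mild one.
3. Add a cross-reference in each direction between 8.1.3.3 and 7.2.4.1.3.

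The cost is wording in three places plus one reference in 7.2.4.1.3, with no new procedures. The downside is that a few patients whose finding would not have been confirmed stop galunisertib, which 7.2.4.1.3 already requires.

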5.6. Rationale for H9H-MC-JBEF Protocol Amendment (c)

H9H-MC-JBEF protocol (b) was amended for the following reasons:

- Phase 2 portion of study: to remove the glioblastoma cohort and update protocol text to reflect this change. Results from 2 recently reported galunisertib trials, Studies H9H-MC-JBAI and H9H-MC-JBAL, have indicated a lack of sufficient efficacy with galunisertib in glioblastoma.
- To clarify the rationale for the changes to the ECHOs in [Attachment 1](#) made in protocol amendment (b) (see Section 5.5 bullet 6): the requirement for ECHO (echocardiography) at the 30-day follow-up visit was restored into the protocol as this requirement had been inadvertently removed during Amendment A; for the Phase 2 portion, clarification was provided that imaging is to be collected centrally.
- [Attachment 2](#): to add hepatitis B surface antigen testing to match what is already stated in Attachment 1, to add that hepatitis testing at baseline will be assayed by a local and a Lilly-designated laboratory and during the trial will be performed by a Lilly-designated laboratory; and to clarify in Attachment 2 the footnotes.
- [Attachment 4](#): to add a ± 10 -minute window to the blood biomarker collection on Cycle 1 Day 1.

Minor editorial corrections or clarifications may have been made but not noted. A detailed list of changes may be found in [Attachment 13](#).

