Treatment decisions related to patient management and whether to treat a patient with advanced refractory solid tumours with additional cycles of study therapy will be based on RECIST version 1.1 for all study patients except patients with glioblastoma, for whom treatment decisions will be based on RANO criteria.

[figure not shown]
At the sponsor's discretion, scans and measurements may be collected and reviewed by independent radiologists using RECIST version 1.1/RANO criteria at a later date, or at any time during the study.

The planned duration of treatment is not fixed; patients will remain on study treatment until they fulfil 1 of the criteria for study discontinuation ([Section 6.3](#)). Patients demonstrating a benefit from treatment may continue on combination therapy if the patient and investigator feel that the patient is benefiting from treatment. If a patient experiences an AE that requires the patient be discontinued from 1 of the 2 study drugs, the patient should continue on the other study drug

(Section 7.2.4). Landmark analysis of all study patients will occur at 6, 12, and 18 months, and OS will be assessed at the end of trial.

Patients who have discontinued from combination treatment will enter the Safety Follow-Up period with visits at approximately 30 and 100 days. If the patient has only discontinued from 1 of the 2 study drugs, the patient will continue on treatment until they discontinue from the second drug, at which time they will enter the Safety Follow-Up period as noted above. If patients have discontinued treatment for reasons other than disease progression, tumour assessments should continue every 8 weeks until disease progression occurs, initiation of a new anticancer therapy, the patient dies or is lost to follow-up. Patients will be followed for survival approximately every 12 weeks (± 7 days) until death or end of trial. This follow-up may occur through a phone call, email, or visit by the patient or the patient's caretaker.

Refer to [Attachment 1](#) for the study schedule.

Abbreviations: approx = approximately; BID = twice daily; IV = intravenous; HCC = hepatocellular carcinoma; n = number of patients; NSCLC = non-small cell lung cancer; Q2W = every other week; QD = daily; TBD = to be determined.

Figure JBEF.6.1. Study H9H-MC-JBEF design.

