Palliative radiotherapy will be allowed. No toxicities have been observed when radiotherapy has been added to galunisertib. The potential for overlapping toxicities with radiotherapy and nivolumab currently is not known. Therefore, palliative radiotherapy is not recommended while receiving nivolumab. If palliative radiotherapy is required, then nivolumab should be withheld for at least 1 week before, during and 1 week after radiation. Patients should be closely monitored for any potential toxicity during and after receiving radiotherapy, and AEs should resolve to Grade ≤ 1 prior to resuming nivolumab. In the NSCLC cohort, nontarget brain lesions and nontarget bone lesions without lung tissue included in the planned radiation field may receive palliative radiotherapy. Details of palliative radiotherapy should be documented in the source records and eCRF. Details in the source records should include: dates of treatment, anatomical site, dose administered and fractionation schedule, and AEs. If warranted, symptoms requiring palliative radiotherapy should be evaluated for objective evidence of disease progression.

In addition, any disease progression requiring other forms of specific antitumour therapy will also necessitate early discontinuation from the study. Appropriate documentation for all forms of premedications, supportive care, and concomitant medications must be captured on the CRF. Replacement hormonal therapy initiated before study entry will be allowed.

Concomitant use of strong CYP3A4 inhibitors and inducers is prohibited in Phase 1b to minimise the influence of potential drug interactions on the galunisertib/nivolumab combination. See [Attachment 12](#) for guidance on restricted medications.

All concomitant medications should be recorded throughout the patient's participation in the study.

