8.1.2.2.3. Follow-Up Visits

All AEs and SAEs, regardless of relatedness to study drug(s) or protocol procedures, occurring during the safety follow-up visits occurring at approximately 30 and 100 days after last dose of combination treatment must be reported to Lilly or its designee ([Attachment 1](#)).

For the Phase 1b part only, following the safety assessments (which occur after the patient discontinues from study treatment) which mark the end of the follow-up visit, the patient will be discontinued from the study, unless there is an ongoing AE or SAE that is possibly related to study drug or protocol procedures. In this instance, the patient should be followed in subsequent follow-up visits until the event is resolved, the event is no longer considered to be drug-related, the event becomes stable or returns to baseline, a new treatment is initiated for the patient, or the patient dies or is lost to follow-up.

For the Phase 2 part only, following the safety assessments (which occur after the patient discontinues from study treatment) which mark the end of the follow-up visit, the patient will be followed only for survival (overall and 6, 12, and 18 months), unless there is an ongoing AE or SAE that is possibly related to study drug or protocol procedures. In this instance, the patient should be followed in subsequent follow-up visits until the event is resolved, the event is no longer considered to be drug-related, the event becomes stable or returns to baseline, a new treatment is initiated for the patient, or the patient dies or is lost to follow-up.

If it is deemed to be in the best interest of the patient to start a new anticancer treatment prior to the scheduled end of the follow-up visit, the follow-up visit duration may be shortened. In this case, the follow-up assessments should be completed prior to the initiation of the new therapy.

After the follow-up visits, AEs are not required to be reported unless the investigator feels the AEs were related to either study drug, drug delivery system, or a protocol procedure. If an investigator becomes aware of SAEs believed to be related to protocol procedures or study drug, the investigator should report the SAE to the sponsor, and the SAE will be entered in the Lilly Safety System.

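### Three pieces of protocol wording on the 30-day visit and on leaving the study contradict the safety and survival follow-up that the analyses rely on

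*Protocol*

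**What the plan says.** **30-day visit.** Protocol 8.1.3.3 (Echocardiography/Doppler) deals with a patient who had no significant cardiac finding at an assessment in the previous 30 days. If that "patient has started another treatment, 30-day follow-up visit will not be performed". The ECHO rows of Attachment 1, in the Phase 1b and the Phase 2 schedule, carry the same rule: "patient has started another treatment, 30-day FUP Visit will not be performed".

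Other text on that visit:
- 6.2: patients who stop combination treatment "will enter the Safety Follow-Up period with visits at approximately 30 and 100 days".
- 8.1.2.2.3: if new anticancer treatment has to start early, follow-up may be shortened, but "the follow-up assessments should be completed prior to the initiation of the new therapy".
- Attachment 1, chest-imaging rows: under a near-identical condition, the "30-Day FUP Visit MRI or CT scan with contrast will not be performed".
- 5.6, on the amendment history: "the requirement for ECHO (echocardiography) at the 30-day follow-up visit was restored into the protocol".

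**Progression and new therapy.** Section 7.5 says that "any disease progression requiring other forms of specific antitumour therapy will also necessitate early discontinuation from the study". Section 6.3.2 treats the need for another effective agent as a reason to stop study drug. Section 6.2 states "Patients will be followed for survival approximately every 12 weeks", continuing to death or trial end, and 6.2.4 defines long-term follow-up in the same way.

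**Phase 1b.** Section 8.1.2.2.3 discontinues Phase 1b patients from the study once the safety follow-up assessments are done, unless a possibly related event is ongoing. Only the Phase 2 paragraph goes on to survival follow-up. Section 5.4 lists the inclusion of Phase 1b patients in OS as a change made in amendment (a). Section 6.2 applies the landmark analysis to all patients, and the Phase 1b schedule has a survival row.

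**The concern.** Safety is the primary endpoint and runs to about 100 days after treatment (Protocol 8.1). SAP 6.9.3 summarises serious adverse events to 30 and 100 days, and SAP 6.9.2 counts deaths due to adverse events within 30 days of stopping. In Attachment 1 the 30-day visit carries the physical examination, weight, vital signs, cardiac serum markers, haematology, chemistry, ECOG status and CTCAE grading. A rule that cancels the visit rather than the ECHO cancels all of these.

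OS and landmark OS at 6, 12 and 18 months are secondary objectives. SAP 6.7.1 censors a patient not known to have died at the last contact. A patient taken off the study at or soon after progression is therefore censored just as the risk of death rises. That is informative censoring, and it pushes the Kaplan-Meier estimate up. This is a single-arm study, so no control arm carries the same bias.

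**Working it through.** The documents give no figure to reproduce here. The check is a comparison of passages, followed by an illustration under assumed inputs.

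**1. Visit or ECHO?** The sentence in 8.1.3.3 names the visit. It stands in the ECHO section and the ECHO rows, and the sentences around it are about repeat ECHOs and cardiac assessments. The chest-imaging comment uses the same condition and cancels only the scan. Section 5.6 speaks of the ECHO at the visit. All of this points to the ECHO alone. The literal text still conflicts with 6.2 and 8.1.2.2.3, and it appears in three places.

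**2. Study drug or study?** Section 6.3.2 distinguishes discontinuing the drug from discontinuing the study. For much the same trigger as 7.5 it names the drug. So 7.5 conflicts with 6.3.2, and also with the survival follow-up in 6.2 and 6.2.4.

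**3. Phase 1b.** Taking these patients off the study after safety follow-up conflicts directly with 5.4, with 6.2 and with the survival row of their own schedule. Unlike the 7.5 rule, it does not depend on progression.

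**4. Illustration of the OS effect.** Every input in this step is an assumption.
- Progression hazard λ = ln 2 / 3 = 0.231 per month (median 3 months).
- Death hazard per month before and after progression (h1, h2): scenario A 0.02 and 0.11; scenario B 0.03 and 0.105.
- A fraction f of progressors is censored at a delay d after progression, with d = 0 or 100 days (3.29 months).

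With a = λ + h1:
- Alive and progression-free: P0(t) = exp(−a t)
- Alive after progression: P1(t) = λ/(a − h2) × [exp(−h2 t) − exp(−a t)]
- True survival: S(t) = P0(t) + P1(t)
- Progressors still under observation: R1(t) = P1(t) − f × exp(−h2 d) × P1(t − d), the last term being zero for t < d
- Kaplan-Meier limit: KM(t) = exp{−∫ (h1 P0 + h2 R1)/(P0 + R1) du}, integrated numerically from 0 to t

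True 12-month OS:
- A: P0 = exp(−0.251 × 12) = 0.049; P1 = (0.231/0.141) × (0.267 − 0.049) = 0.357; S = 40.6%.
- B: P0 = exp(−0.261 × 12) = 0.044; P1 = (0.231/0.156) × (0.284 − 0.044) = 0.355; S = 39.9%.

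Apparent 12-month OS (A / B):

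| f | censored at progression | censored 100 days later |
|---|---|---|
| 0 | 40.6% / 39.9% | 40.6% / 39.9% |
| 25% | 43.1% / 41.9% | 41.6% / 40.7% |
| 50% | 46.9% / 44.9% | 43.0% / 41.8% |
| 75% | 54.4% / 50.7% | 45.1% / 43.5% |

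The upward bias is about 2 to 14 points if censoring falls at progression, and about 1 to 4 points if it falls about 100 days later.

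**The case against.** The strongest reply is that the plan as a whole already supplies the follow-up. Much of this stands.

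- The visit rule needs two conditions together: a clean cardiac assessment within 30 days and a new treatment. ECHOs are scheduled every 8 weeks, so if the assessment meant is the ECHO, not every patient who switches qualifies.
- Section 8.1.2.2.3 asks for the assessments before new therapy starts. The 100-day visit repeats most of them, and reporting of adverse and serious adverse events continues.
- Section 7.5 covers only progression that requires other therapy. Section 7.2.5 allows treatment beyond progression.
- The SAP reads the plan as off treatment, not off study. It lists post-discontinuation therapy (6.6) and stops PFS, but not OS, at subsequent therapy (6.7.1). For registry reporting it counts only withdrawal of consent for all procedures or loss to follow-up as early discontinuation (6.14).
- With about 25 patients per cohort, the 95% half-width around 40% is 1.96 × √(0.4 × 0.6/25) = 19 points, wider than any bias in the table. OS is descriptive.

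A reader might infer that the plan definitely cuts safety and survival follow-up for patients who switch or progress. The documents do not support that, because the passages above keep it. A reader might also take the top of the table as the expected bias. The documents give no rate of switching and no rate of leaving the study, and the visits at about 30 and 100 days make contact beyond progression likely.

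What the reply does not remove is that all three instructions are current text and a site can follow them as written. The Phase 1b sentence is not softened by the Phase 2 paragraph beside it.

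**Conclusion.** The point holds as an internal contradiction in three rules, not as a demonstrated loss of data. Read literally, the ECHO wording drops the 30-day assessments for some patients. Section 7.5 and the Phase 1b sentence of 8.1.2.2.3 end survival contact that 6.2 and 6.2.4 require. The likely direction of the OS bias is upward, provided that the hazard of death is higher after progression. Its size cannot be estimated from the documents. The 42-54% and 41-45% ranges, against a true 40-41%, depend on the assumed hazards, on 25-75% of progressors being censored, and on when the censoring falls. They model censoring tied to progression, so they do not size the Phase 1b effect separately. Nothing in the documents shows that any patient was closed out on this wording. Severity is low.

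**What to change.** Reconcile the passages with five wording edits:
- In 8.1.3.3 and in the ECHO row of each Attachment 1 schedule, state that the omission applies to the ECHO and not to the whole 30-day visit, as the chest-imaging rows already do for the scan.
- In 7.5, separate discontinuation of study drug from discontinuation of the study, consistently with 6.3.2.
- In the Phase 1b paragraph of 8.1.2.2.3, make the same separation, so that the survival follow-up already scheduled in 6.2 and 6.2.4 applies to Phase 1b patients too.

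All three places in the first item need the change, since correcting 8.1.3.3 alone would leave the schedules in conflict with it. The cost is drafting only. No visit or procedure is added.
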